Appendix 2-1 Radiation Dose Estimate

Medical Metrics, Inc.
[name]
[name]

P [contact]
F [contact]
www.medicalmetrics.com

Radiation Dose Estimate for the Arthrocare Eclipse IDE Study

Summary

An estimate of the radiation dose that will be received by patients in the Arthrocare Eclipse shoulder study was prepared based on the available scientific literature. This estimate assumes that standard x-ray positioning and x-ray set-up is used at all sites. There can be substantial site-to-site differences due to the type of equipment and how it is used. This radiation estimate is based on the schedule of radiographic studies as described in the radiographic evaluation protocol.

Literature Estimates

Several peer-reviewed publications provide typical doses for shoulder x-rays. Teeuwisse et al performed an inter-hospital comparison of patient doses[1]. X-ray doses were collected following standardized protocols at 11 hospitals in The Netherlands. Effective doses were reported. They report a median dose of 0.005 mSv for both Neutral AP and AP x-rays of the externally rotated shoulder. The coefficient of variation was 71 to 88% (standard deviation/mean X 100). This is the only publication with view-specific doses. Based on this study, it is assumed that the dose is similar for each of the three x-ray views that will be collected in the Eclipse study. George et al reported typical x-ray doses based on analysis of patient x-ray equipment details collected from six hospitals in the UK[2]. The calculations were verified by comparison to entrance skin dose measurements. They reported suggested dose levels of 0.5 mGy for typical shoulder exams. This dose is expressed in terms of absorbed dose. It is converted to effective dose by multiplying by the weighting factor (1.0) and then by the tissue weighting factor (0.01 for bone). The suggested absorbed dose would therefore result in an effective dose of 0.005 mSv, which is the same as in the Teeuwisse et al study. Mettler et al have published a catalog of effective doses[3]. They provide data for x-ray procedures and this includes all views in a standard exam. They report that the average effective dose is 0.01 mSv for a shoulder procedure. A basic shoulder series consists of AP x-rays with the humerus in neutral as well as in internal and external rotation[4]. The average dose per view would therefore be 0.00333 mSv.

Radiation Dose Estimates for the Study

Based on the publications reviewed, 0.005 mSv will be used as the typical effective dose per x-ray. Each patient would receive 0.015 mSv per visit, and 0.075 mSv for all visits up to and including the 24 month visit. Based on a large study of cancer risk associated with exposure to radiation, it was estimated that the excess relative risk for cancer is 0.97 per Sv[5]. The excess relative risk of the radiation that each patient would receive from participation in the Eclipse study is therefore $0.97 * 0.075 * 1 \text{ Sv}/1000\text{mSv} = 0.000073$. To help place the radiation estimate for the Eclipse study into perspective, a person will be exposed to 0.03 mSv of radiation during a typical coast-to-coast round-trip airplane flight (http://www.radiologyinfo.org/en/safety/index.cfm?pg=sfty_xray). The public is exposed to approximately 3 mSv/y from background radiation[6].

Table 1: Schedule of Radiographic Studies and Examination Intervals and the Typical Doses Expected for each Exam and for the Study Overall (mSV)

RADIOGRAPHIC STUDIES	POSTOP	3 MONTHS	6 MONTHS	12 MONTHS	24 MONTHS	PATIENT TOTAL
AP – Internal Rotation	0.005	0.005	0.005	0.005	0.005	0.025
AP – Neutral Rotation	0.005	0.005	0.005	0.005	0.005	0.025
Axillary	0.005	0.005	0.005	0.005	0.005	0.025
Visit Total	0.015	0.015	0.015	0.015	0.015	0.075

Reference List

Appendix 2-2 Rehabilitation Plan

Postoperative Total Shoulder Arthroplasty Rehabilitation Plan:

Note: The rehabilitation activities and /or schedule may be adjusted as determined by the surgeon.

1. Postoperatively the arm (of target shoulder) is placed in a sling supported by a form-fitting pillow with a waist strap, which immobilizes the upper extremity.
2. Begin wrist, hand, and finger range of motion and grip strengthening on the evening of surgery.
3. Postoperative day one, initiate passive and active-assisted range of motion exercises.
 - a. These activities will include pendulum exercises in a standing position, as well as assisted forward elevation exercises in a supine position with a limitation of 90°.
 - b. Active-assisted external rotation exercises in the supine position are allowed up to 20° of external rotation and again adjusted based on the surgeon's evaluation at the completion of the subscapularis repair.
 - c. The focus of the rehabilitation program is to teach the patient exercises that they can conduct three to four times per day on their own. Assisted devices such as a pulley or a physical therapy baton can be valuable.
4. Provide education to the patient regarding their home exercise program and schedule outpatient physical therapy program prior to discharge.
5. Active exercise is likely to start 10 -14 days after the surgical procedure.
 - a. The major restriction to physical therapy, within the first six weeks, is prohibiting resisted internal rotation or other activities that would put stress on the subscapularis repair such as passive unprotected external rotation performed by the physical therapist.
 - b. If the patient is allowed independent active-assisted external rotation, the subscapularis repair will not be jeopardized.

- c. For the first six weeks the focus is on stretching and improving active range of motion.
6. Once the subscapularis tendon has had adequate time to heal, at approximately six weeks.
 - a. All range of motion including internal rotation are advanced as tolerated.
 - b. The strengthening program is balanced to include both the anterior rotator cuff (subscapularis) and posterior rotator cuff (primarily supraspinatus and infraspinatus).
 - c. Deltoid strengthening as well as scapular muscle strengthening (shoulder shrugs, scapular protraction, scapular retraction, rows, front pull downs) can be gradually incorporated into the patient's rehabilitation program.
7. By three months, it is likely that the patient should be independent with a rehabilitation program. Continued physical therapy after this time period would be a clinical decision by the surgeon.
8. Encourage subjects to pursue both the stretching and strengthening program throughout the entire first year.
9. It is likely that the patients will continue to improve with regards to strength and function for 18-24 months postoperatively.
10. Strength should allow all activities of daily living as well as light recreational activities such as golf, light fitness training, household chores, gardening and swimming in select patients.
11. The final weight-restriction includes no repetitive lifting activities greater than 20 pounds and no repetitive work activities at shoulder level or above on a routine basis.

Appendix 2-3 Surgeon Training

The training program begins with an In-Class session at an ArthroX training center. Training will include didactic and hands-on experience through sawbones and /or cadaveric workshops. During the In-Class session, Trainees will be supervised and mentored by Instructors experienced in the product and surgical Technique. To reinforce the techniques the surgeon has learned, the newly trained investigator/surgeons will have unlimited access to the web-based training materials and access to written material included in the Investigator Training binder.

The objectives that must be met in order to be credentialed on the Eclipse Shoulder are:

1. Attendance at an In-Class Training Session,
AND
2. Completion of two (2) supervised shoulder replacements on sawbones,
OR
3. Completion of two (2) supervised shoulder replacements on cadavers.
AND
4. Demonstrates understanding on the surgical Technique as documented on the Surgical Training Checklist.

Below is a breakdown of the elements of the Surgeon Training Program:

I. In-Class Training Session

- Discussion about Clinical Protocol
 - Patient Selection
 - Indications, Precautions & Contraindications
 - Surgical considerations, implications, perils, pitfalls & recommendations
 - Complications
 - Review of Surgical Video or Cadaver demonstration
- Hands-on Introduction/Review of Instrumentation
- Hands-on Training
 - Sawbones workshop and/or
 - Cadaver lab for bone

II. Training Materials Available at All Times

III. Online access available to all accepted Trainees

- “DFU” Indications for Use
- Report of Priors
- Eclipse Surgical Brochure
- Surgical Video
- In-Class materials (updated and available after each training session)

IV. In-Class Training Session

- Discussion about Clinical Protocol
 - Patient Selection
 - Indications, Precautions & Contraindications
 - Surgical considerations, implications, perils, pitfalls & recommendations
 - Complications
 - Review of Surgical Video or Cadaver demonstration
- Hands-on Introduction/Review of Instrumentation

Hands-on Training

Appendix 2-4 Schedule of Events

Arthrocare Eclipse Shoulder Prosthesis IDE		Visit 1	Visit 2	Visit 3	Visit 4	Visit 5	Visit 6	Unscheduled
CRF #	Schedule of Events	Day -21 to -2	Day 0	3 months \pm 2 weeks ¹	6 months \pm 1 month	12 months \pm 2 months	24 months \pm 2 months or End of Study	
	Informed Consent ¹	X	X	X	X	X	X	X
01	Demo & History 
 • Kellgren Lawrence • Staging System of Cruess • American College of Rheumatology • SCORE 	X						
02	Medication & Therapy	X ²	X	X	X	X	X	X
03	SF 36	X		X	X	X	X	X ³
04	VAS	X		X	X	X	X	X ³
05	Constant Score	X		X	X	X	X	X ³
06	Physical Exam (VS) 
 • Shoulder Exam • Sensory & Motor Testing 	X		X	X	X	X	X
	Pre-op labs: Pregnancy ⁴	X	X					
07	Enrollment form ⁵	X						
	Patient Education	X	X					
08	Surgery/Operative detail		X ⁷					X
09	AE		X ⁶	X	X	X	X	X
10	Post-operative evaluation			X	X	X	X	X
11	Radiograph ⁹	X ¹⁰	X ¹¹	X	X	X	X	X
	Rehabilitation		X ¹²	X	X	X	X	X
12	Hospital Discharge		X					X
13	Deviation Form	X	X	X	X	X	X	X

14	End of Study						X ¹³	

1 A Month =30 days
 
2 Informed Consent (ICF) is obtained and signed prior to any study related procedures and a revised ICF is signed at the next study visit prior to any new or revised study related procedures.
 
3 Medication /Therapy Form will document at least 3 months of conservative treatment as required per Inclusion Criteria
 
4 SF 36, VAS and Constant may be done during unscheduled visit only if one of the required time points was missed, must document in deviation log
 
5 The only Pre-op laboratory require for the study is a pregnancy test if female and with child bearing potential. Pregnancy test may be done at V1 and or V2.
 
6 Data for Enrollment is collected at screening and confirmed at Visit 2 prior to Randomization
 
7 Randomization will occur on visit 2 after Inclusion/Exclusion criteria is confirmed
 
8 Operative detail is collected at Visit 2
 
9 Adverse Events are collected after subject has received treatment
 
10 All Radiographs must be done as per Radiographic Protocol inadequate Radiographs should be repeated within the time point window.
 
11 Radiographs must be available in medical record to validate Inclusion/Exclusion Criteria, if ordered during screening and results available to confirm eligibility prior to Randomization
 
12 The post-operative Radiographs must be done per Radiographic protocol and within 72 hours of surgery.
 
13 The Rehabilitation Plan is initiated on the evening of surgery –Refer to Appendix 2-2
 
14 If subject terminates prior to 24 months all end of study procedure and form are completed as if the subject completed 24 months.
								

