4.1 Study Population

4.1.1 Intention to Treat (ITT) Cohort

The investigator will invite prospective patients to enroll in the study that meet the inclusion/exclusion criteria and have signed the informed consent. All patients randomized to either the investigational device (ArthroX Eclipse™ Shoulder Prosthesis) or the control device (ArthroX Univers™ II Shoulder Prosthesis) will be included in the ITT cohort. Randomization will take place after patients have been screened for inclusion and exclusion criteria. Patients found prior to randomization to not meet all inclusion and exclusion criteria will be defined as screen failures and will not receive the investigational device. These patients will be excluded from the ITT cohort.

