4.1.2 Per Protocol (Efficacy Evaluable) Cohort

Patients included in the ITT cohort but found to have been randomized in error will be excluded from the Per Protocol (Efficacy Evaluable) cohort. A patient will be considered to have been randomized in error if it is determined that the patient has clinically significant violations of the inclusion or exclusion criteria. Because approval and labeling is sought for patients meeting study inclusion and exclusion criteria, primary non-inferiority testing will be conducted in the Per Protocol (Efficacy Evaluable) cohort. Safety endpoints will be summarized for the Per Protocol cohort for the same reason. However, all adverse events that occur in the study will be reported in safety listings based on the ITT cohort.

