As with any foreign body implant, allergies and other reactions to device material may occur. Patients will be queried about allergies and previous implants; where material sensitivity is suspected, appropriate tests should be made to rule out sensitivity prior to implantation. The Eclipse Shoulder Prosthesis is manufactured from known materials such as Titanium and Cobalt Chrome and coated with Titanium plasma spray (TPS) and Calcium phosphate (CaP); the glenoid component is also manufactured from a known material, Ultra High Molecular Weight Polyethylene (UHMWPE). All of these materials have a long history of clinical use, including in similar medical devices. As the glenoid component is comprised of UHMWPE, there is no risk of metal-on-metal wear, which has recently been determined to cause long-term adverse biologic reactions with certain metal-on-metal hip prosthesis.

Loosening of the implant as a result of changed conditions in load transfer, fatigue wear disassociation of the components, or tissue reaction has been reported to occur (7% aseptic loosening of humeral head). Patients will be assessed for sufficient quantities or quality of humeral head and/or humeral neck bone stock prior to implant via radiograph. Loosening of the implant may also

be caused by inadequate anchoring technique. These risks are mitigated by assuring that the surgeons are properly trained on the specifics of the device, as well as the corresponding surgical procedure.

Specific surgeon training will help mitigate the risks of extreme weakening of the bone structure in the preparation the bone bed, unsuitable implant size selection, inadequate cleaning of the bone bed prior to implantation, excessive use of force in placing or anchoring the implant, creation splintering fractures, or development of bone tears. Additional training regarding the use of only the associated ArthroX delivery system, instruments, and trial prosthesis for implantation will mitigate the risks of dislocation, subluxation, and inadequate scope of movement as a result of failure to achieve optimum positioning of the implant. In addition, proper training on the surgical technique and the positioning of the implants will mitigate the risk of temporary or permanent nerve damage. Surgeon training on the implant utilize will be required of all surgeons in the study, and documentation of surgeon training will be recorded in the site binders (Appendix 2-3 Surgeon Training).

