6.1.3 Enrollment Status

Screening Status:

Subject's that have signed the informed consent and have data collected at Visit 1 will be considered Screened.

Randomized:

Only those patients who meet the inclusion and exclusion criteria.

Treated:

Once implanted the subject status will update to either Implanted - Eclipse or Implanted - Univers II.

Screen Failed:

Screen failures are those subjects who have signed the informed consent and data has been collected at visit 1, but are not eligible or not able to start treatment. Subjects that were screened and randomized but had to have a non study total shoulder replacement will be consider a Screen Fail.

Once the subject is determined to be a "Screen Fail" and the End of Study form is completed (with the reason) in the EDC, the subject status will update to Screen Fail. An enrollment log of all subjects screened for the study. The reason(s) for screen failure will be recorded on the log.

Early Termination:

Subjects that are screened, randomized, and implanted with the Univers II or the Eclipse but drop out prior to 24 months (720 days +/- 60days) will be considered Early Termination.

Potential reasons for "Early Termination" may include, but are not limited to:

- Subject participation in a clinical trial is voluntary. The subject may discontinue participation (refuse all subsequent testing and follow-up procedures) at any time without penalty or loss of benefits.
- The investigator may terminate the subject's participation without regard to the subject's consent if the investigator believes it is medically necessary and in the best interest of the subject.
- Lost to Follow-up: The subject does not complete the 24 month follow-up but has not "officially" withdrawn from the study.
 - Failure to return for follow-up visits is not a criterion for withdrawal.
 - In order to consider a subject lost to follow-up, site personnel should make all reasonable efforts to locate and establish communication with the study subject. All attempts should be

documented within the source documents, indicating date, time, method, and site personnel.

- A minimum of three documented attempts should be made without response from the study subject in order to classify a subject as lost to follow-up.

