9.2 Adverse Event Documentation

Adverse event information will be collected on all subjects. All adverse events must be reported in the source documents and in the EDC. Adverse events will be evaluated by the investigator and differentiated by:

- Seriousness, as defined in Section 9.1.2
- Severity of the event, defined below.
 - **Mild:** Awareness of signs and symptoms, but easily tolerated; are of minor irritant type, causing no loss of time from normal activities; symptoms would not require medication or a medical evaluation; signs and symptoms are transient.

- **Moderate:** Discomfort severe enough to cause interference with usual activities; requiring treatment, but not extended hospitalization or intensive care for the subject.
- **Severe:** Incapacitating with inability to do work or usual activities; signs and symptoms may be systemic in nature or require medical evaluation and/or treatment; requiring additional hospitalization or intensive care (prolonged hospitalization).
- Relatedness to the device or procedure, defined as:
 - **Unrelated:** AE is due to the underlying disease state or concomitant medication or therapy not related to the study-specific devices or procedures.
 - **Probably not Related:** AE had minimum or no temporal relationship to the study-specific devices or procedures and/or more likely alternative etiology exists.
 - **Possibly Related:** AE had a strong temporal relationship to the study-specific devices or procedures and alternative etiology is equally or less likely compared to the potential relationship to the study-specific devices or procedures.
 - **Probably Related:** AE had a strong temporal relationship to the study-specific devices or procedures and another etiology is unlikely.
 - **Unknown:** Relationship of the AE to the study-specific devices or procedures and alternative etiology is unknown.

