10.7.2 Adverse event detail listings

Adverse events listings will be provided for all patients in the ITT cohort and will provide details regarding adverse event type, relation to shoulder procedure, action taken, and clinical outcome. Separate listings will be constructed for adverse events with “definite” relationship to the device, “severe” adverse event, “severe device-related”, serious adverse events, and for all adverse events. The listing for all adverse events will be sorted by adverse event type.

Additional listings will be provided that include all adverse events among procedures requiring revision, removal, or replacement and all adverse events among patients who died.

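### The schedule starts adverse event collection at treatment, so subjects randomised but not given a study total shoulder have no assured collection, although ITT safety listings are promised

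*Combined protocol and SAP*

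**What the plan says.** **Start of collection.** Note 9 of Appendix 2-4 (Schedule of Events) says "Adverse Events are collected after subject has received treatment". Note 7 says "Randomization will occur on visit 2 after Inclusion/Exclusion criteria is confirmed", so assignment precedes the operation on day 0. Under the status Treated, section 6.1.3 says "Once implanted the subject status will update to either Implanted - Eclipse or Implanted - Univers II".

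**Subjects randomised but not given a study total shoulder.** Section 6.1.3 labels a randomised subject who has to have a non-study total shoulder replacement a Screen Fail. The paperwork it names is the End of Study form with a reason and a log entry. Section 4.3 removes from the study any subject whom the surgeon converts to a hemi-arthroplasty. Early Termination, the status for leaving before 24 months, is defined in 6.1.3 only for implanted subjects.

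**Whose events are promised.** Section 4.1.1 defines the ITT cohort by assignment: "All patients randomized to either the investigational device" or to the control belong to it. Section 4.1.2 states that "all adverse events that occur in the study will be reported in safety listings based on the ITT cohort". Section 10.7.2 repeats this: "Adverse events listings will be provided for all patients in the ITT cohort". Section 9.2 says "Adverse event information will be collected on all subjects", and 5.1 has subjects monitored for adverse events from day 0 to 24 months.

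**The concern.** A rule that starts collection at implantation cannot by itself supply listings for a cohort fixed at randomisation. The subjects between those two points are those whose planned operation did not go ahead as intended, and the reason may itself be an adverse event. Section 5.1 lists among the hazards that surgeon training should reduce "excessive use of force in placing or anchoring the implant, creation splintering fractures, or development of bone tears". Such an event could plausibly end in a conversion.

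Site staff who work from the schedule could reasonably conclude that no adverse event form is due for a subject who was never implanted with a study total shoulder and has been closed out. An event not recorded at the time may be hard to recover later.

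More than the listings is at stake. Section 4.1.2 removes from the Per Protocol cohort only subjects randomised in error, meaning those with clinically significant eligibility violations. An eligible subject who was not implanted stays in the cohort used for the safety summaries, and may have no safety record there either.

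**Working it through.** This is a question of consistency, so the main check is to follow each type of subject through the rules.

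| After randomisation on day 0 | Status | Adverse event step described | ITT (4.1.1) | Per Protocol (4.1.2) |
|---|---|---|---|---|
| Study total shoulder implanted | Implanted (6.1.3) | Yes: Visit 2 review and every later visit | In | In, unless randomised in error |
| Non-study total shoulder replacement | Screen Fail (6.1.3) | None specific to this group | In | In, unless randomised in error |
| Converted to hemi-arthroplasty | Out of the study (4.3) | None specific to this group | In | In, unless randomised in error |

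Rows two and three are inside both cohorts and outside any stated collection step. The label adds to the risk. Section 4.1.1 uses screen failure for patients found ineligible before randomisation and excludes them from ITT, while 6.1.3 applies the same term to subjects already randomised. A program that drops everyone with that status would also drop ITT members.

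The same check for **intraoperative events in implanted subjects** gives a different answer. The schedule has an adverse event entry at Visit 2, the day of surgery. Section 6.3 places the review next to the operative details. Section 9.3 asks at each contact about everything since the previous one, which spans the operation. Section 10.7.1 counts events in a pre-discharge interval with no lower limit at implantation. A review held after surgery does not exclude what happened during it, so these events are probably captured.

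**Size.** The plan gives no rate of non-implantation, so only an illustration is possible.
- Inputs from 10.4: 98 control and 196 Eclipse evaluable subjects, with a 15% allowance for losses.
- 98 / 0.85 = 115.3, rounded up to 116; 196 / 0.85 = 230.6, rounded up to 231; 116 + 231 = 347, which reproduces the plan's randomised total.
- Assumed non-implantation rate: 0.5% to 3%.
- 231 × 0.005 = 1.2 and 231 × 0.03 = 6.9, so about 1 to 7 Eclipse subjects.

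This counts subjects whose collection is not assured. Some may have had no adverse event, and some who had one may still have it recorded.

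**The case against.** The strongest reply is that one schedule note should not override the body of the protocol. Section 9.1.1 defines an adverse event as any undesirable experience during the study, 9.2 covers all subjects, 5.1 starts at day 0, and 9.3 requires serious events to be reported within 24 hours whatever the implant status. Note 9 does not say that nothing else is collected. Received treatment could mean having had the operation, and a subject given a Univers II hemi-arthroplasty might be read as implanted. Section 6.6 and note 14 also require end-of-study procedures, which include an adverse event review, when a subject stops early.

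Much of this stands. It rules out the reading that the plan forbids or omits collection before implantation, and it disposes of any claim that intraoperative events in implanted subjects are lost. It does not close the gap for the other two groups. Section 6.6 and note 14 do not say whether they reach a Screen Fail or a subject removed under 4.3, and 6.1.3 mentions only the End of Study form for the former. That the body text points one way and the schedule and status rules another is itself the defect.

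A reader might also infer that the ITT listings will hold only implanted subjects, that the missing events would be the most serious and device-specific ones, or that the comparison between arms is biased. The documents support none of these. Sections 4.1.2 and 10.7.2 promise the contrary on the listings. The device-related events named in 9.1.3 include loosening, dislocation and stiffness, which can arise after implantation. The two humeral components are fixed differently, so a loss need not be balanced, but nothing shows that it would be unbalanced. A surgeon may also convert to a hemi-arthroplasty under 4.3 without any adverse event.

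**Conclusion.** The point holds in a limited form and should be corrected. Read with 6.1.3 and 4.3, note 9 leaves adverse event collection unassured for subjects randomised on day 0 but not given a study total shoulder. That is inconsistent with 5.1, 9.2 and the ITT listings in 4.1.2 and 10.7.2, and these passages must be reconciled. The same gap can reach the Per Protocol safety summaries.

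The conclusion rests on reading received treatment through the protocol's own status term, Treated. On the broader reading, the status and removal rules still give these subjects no described adverse event step.

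The number affected is unknown. The 1 to 7 Eclipse subjects depend wholly on the assumed 0.5% to 3%, and it would be wrong to quote them as 1 to 7 lost events. The sample size and the primary Composite Clinical Success test are not directly affected.

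**What to change.** 1. Replace note 9 of Appendix 2-4 with: *Adverse events are collected from randomisation at Visit 2 for every randomised subject, including intraoperative events.* For implanted subjects this only makes explicit what the plan probably intends.
2. In 6.1.3 and 4.3, require the existing Surgery/Operative Detail and adverse event forms for every randomised subject not given a study total shoulder, before the End of Study form is completed. Reported events should be updated as 9.3 already requires.
3. In 10.7.2, state that these subjects are included in the ITT listings whatever their status label.

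The cost is wording in four places and two existing forms for what is probably a small number of subjects. The reported event count may rise slightly. No new form or visit is needed, and no rule on clinical management changes.
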